## 4 TRIAL DESIGN

Pragmatic multi-centre two-arm randomised, superiority trial with parallel groups (allocated on a 1:1 ratio) with an embedded qualitative evaluation and cost-effectiveness evaluation.

## 5 TRIAL SETTING

This is a multi-centre randomised controlled trial, taking place in physiotherapy services based in NHS hospitals across the UK. We expect to open six sites, with scope of increasing this number if required. To ensure inclusivity we will work with a range of NHS hospitals serving diverse communities in rural and urban communities. At each site there will be two physiotherapists who will be trained to deliver the CMT intervention. Participants in the CMT arm of the trial will receive the CMT intervention at one of these research sites.

All sites are expected to be recruiting sites, undertaking all research activities. At each site, the CMT intervention will be delivered within a dedicated physiotherapy clinical space. However, in the case that a particular trust is unable to provide space for intervention delivery, a GP practice or community space (such as a private room in a community centre) within close proximity of the research site, will be used to deliver the

CMT intervention. The intervention may also be delivered within a dedicated clinical space at the University of Salford which is close to one of the research sites.

## 6 TRIAL TREATMENTS

### 6.1 Details of the control intervention

For patients who have not benefited from NICE-recommended therapeutic exercise, usual care includes treatments such as pharmacological management, intra-articular steroid, and surgery [4]. Participants in the control arm will be instructed to access this care as they would if they were not involved in the trial.

### 6.2 Details of the Cognitive Muscular Therapy (CMT) intervention

Participants in the CMT arm will be instructed to access care as they would if they were not involved in the trial and will also receive the CMT intervention. This section provides a complete description of the CMT intervention, covering each of the items proposed in the TIDierR (Template for Intervention Description and Replication) framework [29]. The CMT intervention was developed at the University of Salford between 2018-2023 [18] through an iterative co-design process. The aim of CMT is to improve coordination of the knee muscles, reduce mechanical loading on the knee and change psychological responses to pain. CMT specifically targets overactivity of the knee muscles because this patterns has been linked to increased compressive loads on the joint surface [11], accelerated disease progression (cartilage loss) [12], increased likelihood of knee replacement at 5-year follow up [30] and increased pain [31, 32]. The CMT intervention is delivered by a physiotherapist across seven individual clinical sessions, each lasting approximately 1 hour. Intervention sessions are typically delivered weekly, but this depends on participant availability and gaps of 2-3 weeks between some intervention sessions are acceptable.

#### Equipment required to deliver the intervention:

The intervention requires a clinical space with an adjustable height plinth and chair. In the latter stages of the intervention, access to a staircase is required (to practice stair ascent/descent) along with a space to practice walking. The clinical space needs to be equipped with a desk, computer and electromyography (EMG) system. The EMG system is used to provide biofeedback, providing a visual representation of the level of activity in the quadriceps muscles during specific activities (stages of the protocol). For this study, we will use the Biometrics (Newport, UK) wireless EMG system within its intended statement of use. This system is CE marked and meets EU/UK Medical Device Regulation (207/745). We have selected this EMG system because of its low cost, ease of clinical use and reliability (tested in previous studies run by the University).

The CMT intervention comprises five components: Understanding knee pain, General relaxation, Postural deconstruction, Contextual triggers and Functional integration.

#### Component 1 (Understanding knee pain):

The aim of the first component is to challenge inappropriate illness beliefs and to enable the participant to reconceptualise the mechanisms which are likely to underlie knee OA pain. During this component the

participant watches three videos. After each video, there is a discussion with the physiotherapist to challenge inappropriate beliefs and to ensure that concepts have been fully understood. The first video is designed to challenge beliefs which are inconsistent with the therapeutic focus of CMT. Key beliefs relate to the idea that activities which exacerbate pain should be avoided, that knee pain is always the result of structural damage and that continued muscle strengthening is required to maintain knee function once knee OA has been diagnosed. The second video explains how increased activity of knee muscles can negatively affect anatomical structures around the knee. The final video explains how psychological factors, such as pain-related fear and pain catastrophizing are likely to shape the pain experience, integrating principles from therapeutic neuroscience education. In the second and third videos, participants are taught about the need to become aware of habitual responses to pain and to become aware of how pain can trigger muscle tension and/or pain-related fear which can then further exacerbate knee pain.

#### Component 2 (General relaxation):

The aim of the second component is to raise awareness of elevated low-level activity in the quadriceps muscles and in the muscles of the torso, hips and shoulders. Participants begin by learning diaphragmatic breathing in supine to gain a sense of elevated muscle activity in the abdominal wall. Passive limb motions in supine are then used to raise awareness of increased muscle activity around the hips and shoulders. EMG biofeedback (electrodes placed on vastus lateralis) is then used to guide relaxation of the quadriceps muscles, first in lying, then sitting and then during supported standing (leaning against the plinth). In each position, the physiotherapist guides the participant to relax the quadriceps through manipulation of the patella. Through this process, participants gain experiential learning of what it feels like to relax the anterior knee muscles.

#### Component 3 (Postural deconstruction):

The third component of the intervention focuses specifically on improving the organisation of postural tone (low-level muscle activity which supports the body against gravity). This focus on postural tone is critical as increased flexor tone can drive compensatory activation of the extensor muscles, including activation of the quadriceps muscles, which will increase mechanical loading on the knee [18]. To understand this concept, participants watch an animated video which depicts a 'tug-of-war' between flexor and extensor muscles. They are then taught to recognise patterns of compensatory extensor tone in spine, hips and knees while transitioning from a flexed to an upright position. Guided by the physiotherapist, they learn to identify a 'tension point' where extensor compensation becomes apparent and where the quadriceps muscles activate (visualized using EMG). Working in a flexed position allows participants to appreciate the links between flexor tone, extensor compensation and unwanted activation of the knee muscles. Through hands-on guidance, participants learn to increase costovertebral motion, increase range of trunk rotation, and to lengthen abdominal and neck muscles, thereby reducing flexor tone. At the end of this component, the aim is for participants to stand upright without compensatory extensor tone and with relaxed quadriceps muscles.

#### Component 4 (Contextual triggers):

In the fourth component participants learn that anticipating pain-provoking tasks can become associated with increased flexor tone and inappropriate contraction of the quadriceps muscles. They also learn that common daily activities, such as working at a computer, may trigger elevated flexor tone. To address these 'conditioned' responses participants are guided to mentally rehearse specific situations without triggering undesired increases in abdominal tone (monitored through visual inspection of abdominal wall excursion) or quadriceps activity (monitored via EMG). In the final stages of this component participants learn to initiate potentially pain provoking activities, such as stair ascent/descent without inappropriate activation of the quadriceps muscles.

Component 5 (Functional integration):

The final component focuses on integrating the learning from the previous four components. The goal is to enable participants to perform a full range of functional activities with minimal pain. Participants select activities from a comprehensive set that covers the full range of tasks assessed by the WOMAC questionnaire score [19]. This includes standing, walking, stair ascent/descent, bending, dressing etc. Guided by the physiotherapist, the participants practice performing each task with an optimal pattern of postural tone and without inappropriate activation of the quadriceps muscles.

Intervention delivery, home practice & self-management:

During the seven hour-long sessions, the physiotherapist works through a clearly delineated protocol which follows the intervention structure described above. Each stage of the protocol allows for tailoring to individual participant needs, e.g. psychological factors/different learning styles. Between each clinical session, participants are given 3-4 specific 'challenges' which require them to improve awareness of muscle tone, improve their capacity to relax the quadriceps muscles and change their psychological responses to pain. After each session, the participant is provided with a summary sheet which lists learning points and summarizes each challenge. To facilitate this learning/practice, participants are provided with access to an online platform which includes both written documents and animated videos. If participants are unable to engage with the online platform (e.g. no access to the internet), they are provided with a paper booklet. Following completion of the treatment, the aim is that the new muscle coordination patterns become habit. Therefore, while participants are encouraged to continue to practice the different challenges, the primary aim is that they have skills and knowledge to self-manage their knee OA, including any pain flare ups, as they go about their daily life.

Risk assessment:

This CMT intervention is very low risk. To date, we have delivered implementations of the CMT intervention to over 200 participants with no adverse events. Nevertheless, we have created a risk assessment (see 'CMT for musculoskeletal conditions - risk assessment') which will be used as part of the training that the CMT physiotherapists receive (see sections below). This includes standard precautions in rehabilitation, such as minimising infection risk, checking equipment regularly and ensuring there are no hazards which could cause a trip or fall. In addition, the physiotherapist will monitor for any allergic skin reaction to the EMG sensors and monitor for any dizziness which may result from inappropriate practice of the CMT breathing exercises.

### 6.3 Identification of physiotherapists who will deliver the CMT intervention

We will identify two physiotherapists who will deliver the CMT intervention at each of the research sites. We aim to set up a minimum of six research sites (12 physiotherapists) but may look to increase the number of sites if recruitment is lower than anticipated. These physiotherapists will be identified through NHS departments. To be included in the trial, we will ensure that all physiotherapists meet the following criteria:

1. Have at least 3 years' experience of treating patients with chronic musculoskeletal pain on the NHS.
2. Currently employed in the NHS to treat patients with chronic musculoskeletal pain.
3. Be willing to undertake the CMT training (detailed below), including online and face-to-face training.
4. Be available for at least 3 hours per week for a period of 1 year to deliver the CMT intervention.
5. Not involved in delivery of care to control participants

## 6.4 Physiotherapist training to deliver the CMT intervention

Training and assessment of the 12 physiotherapists will follow a two-stage process. The first stage is an online course, comprising of 15 separate modules, each taking 30-90 minutes to complete. These modules cover underpinning research in knee OA, background theory to CMT, principles of psychologically informed physiotherapy and the use of EMG biofeedback. The latter modules focus specifically on the specific protocols which are used to deliver the CMT intervention. During the online modules, animated videos are used to convey intervention theory and treatment footage used to explain the hands-on techniques used to guide muscle re-education.

Once the online course is completed, physiotherapists attend three face-to-face workshops, each lasting one day. At these workshops, the physiotherapists gain confidence at using CMT intervention techniques, following the CMT protocols and in using EMG biofeedback. During the workshops the physiotherapists develop their skills by practicing on both medical actors and real patients with knee OA. While the first day is more introductory, by the end of the second day physiotherapists complete a competency assessment to certify that they have sufficient knowledge to deliver CMT to patients with knee OA.

To identify patients who will attend the face-to-face workshops, we will recruit via non-NHS mechanisms (social media, poster, university database) following the procedures described in Section 8.1. This will include the use of a separate web page (<https://hub.salford.ac.uk/volunteer-for-research/studies/bepko3-training/>) to provide participant information and collect screening data. Note that the same web screening form as described later (see 'Web screening form') will be used to collect these data. Following our standard procedures, participants will be provided with the training information sheet (see 'Participant information sheet (Physiotherapist training)') and given at least 24 hours to read and understand the information. They will then be consented by a member of the research team using the training consent form (see 'Consent form (Physiotherapist training)'). This consenting will follow the same process as described in Section 8.3.

Consenting participants will receive the CMT treatment from the research team before/after the training day and may receive some treatment during the training day. They will also be asked if they would be happy to be recorded during treatment (this recording is optional) and for this footage to be used for future online training of health professionals. If participants do consent to being recorded, the video recording will be stored in a secure server managed by the University of Salford, all identifying features will be removed and then they will sign a video release form (see 'Video release form'). If videos are retained for future training, participants will receive a payment of £100. If videos are not used, they will be permanently deleted. We will not collect outcomes from participants who are consented for physiotherapist training but will retain contact details for the duration of the trial so that they can be sent a summary of the study findings.

To provide the physiotherapists with the opportunity to practice delivering CMT after the second face-to-face workshop, we will provide them with the option of consenting patients to receive the CMT treatment using the training participant information sheet (see 'Participant information sheet (Physiotherapist training)') and 'Consent form (Physiotherapist training)'). These patients will be identified by the physiotherapist as an individual who is currently under their care for knee OA and who is happy to receive the CMT treatment. We will ensure that any physiotherapist who consents has completed mandatory GCP training and that the screening and consenting processes described in the protocol are followed. The consent form and contact details of the participant will be stored by the research team. Again, we will not collect outcome data from participants consented for physiotherapist training, however, we will retain contact details for the duration of

the trial so that they can be sent a summary of the study findings. To accommodate different learning styles, we recognise that some physiotherapists may not feel it necessary to practice independently on patients and will be happy to continue to practice working through the CMT protocols with professional colleagues.

After a period of 1-3 months (depending on physiotherapist preference and timing of recruitment for the main clinical trial), physiotherapists will be invited back for a third (final) face-to-face workshop. At this workshop, the research team will go through any aspects of the CMT protocols which the physiotherapists have found particularly challenging to understand/deliver and then carry out a final competency check. For this final check, physiotherapists will be expected to have in-depth knowledge of the protocols and have memorised every stage.

Experience from previous trials shows that physiotherapists require exposure to a range of different presentations of knee OA before they can be fully confident in adapting and applying the CMT protocols for different patients. Therefore, we propose to provide direct supervision for each physiotherapist when they treat the first 3-4 participants. This supervision will be provided by a member of the research team either through direct observation or through video recording and subsequent follow-up. We recognised that some participants may not feel comfortable with being videoed and therefore we will make this optional. All recordings will be stored securely on a University of Salford server and deleted once analysis has been completed, typically within 2-3 weeks of the recording.

## 6.5 Treatment log

The physiotherapist will record the date and length of each of each treatment sessions for every participant in the CMT arm. These data will be transferred from the treatment log to the secure trial database by the trial manager (or another member of the team who is not blinded to group allocation) to provide a measure of attendance (date of first intervention session, date of final intervention session and total number of sessions attended). In addition, the following data will be recorded during the CMT treatment by the treating physiotherapist:

*Table 1: Treatment log*

	Time point	Description	Collected by
Clinical notes	After each clinical session	A pro forma will be used to summarise clinical presentation and capacity to engage with intervention techniques	Physiotherapist
Participant engagement score	At start of clinical sessions 2-7	
The physiotherapist will assess:
 
 
1. Engagement with the online learning platform
 
2. Written reflections on home practice (patient summary sheet)
 
3. Competence and understanding of previous week's challenges (home practice)
 
 
Based on this assessment, the physiotherapist will determine a weekly engagement score:
 
 
1. 0 = not engaged
 
2. 1 = low engagement
 
	physiotherapist

		3. 2 = full engagement	
--	--	------------------------	--

The weekly engagement score will be recorded in the clinical notes but will not be used as part of any analysis of trial outcomes. If scores are consistently below 2 then the physiotherapist will spend time at the end of each clinical session discussing barriers to engagement and creating an action plan with the participant to improve engagement and home practice.

## 6.6 Assessment of intervention fidelity

Intervention fidelity will be assessed for each physiotherapist who delivers the CMT intervention. This assessment will be carried out after they have completed treatment on the first 3-4 participants under supervision of a member of the research team (see above). For each physiotherapist, we will video record at least two intervention clinical sessions for each of the seven clinical CMT sessions (14 recordings per physiotherapist). Using a 25-point checklist, a member of the research team will score physiotherapist's ability to deliver each stage of the CMT protocols. After scoring the full set of 14 recordings, the final score will be converted to a percentage.

## 6.7 Potential for contamination

CMT is not currently available on the NHS and is only delivered through research studies which are being run by the University of Salford. Therefore, at present, it is not possible for patients outside this trial to access this treatment. However, this situation may change during the trial as we may offer training in CMT to private physiotherapists. In this situation, participants in the control arm could potentially access CMT through private providers, resulting in contamination. To mitigate against this, we have omitted the name of the CMT intervention from the participant information sheet. We will also collect information on physiotherapy accessed during the trial through the healthcare resource questionnaire (see 'Healthcare resource use questions').

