## 7.2 Exclusion criteria

- BMI>33 (as increased subcutaneous fat prevents collection of EMG signals)
- Inflammatory arthritis including rheumatoid arthritis, psoriatic arthritis, ankylosing arthritis, enteropathic arthritis, lupus, septic arthritis or gout.
- Diagnosis of a widespread pain condition, such as fibromyalgia
- Neurological disorder, such as multiple Sclerosis, cerebral palsy or previous stroke (with ongoing neurological deficit)
- Diagnosis of dementia and score >17 on the Telephone-Mini mental state examination (T-MMSE) for cognitive impairment [33]. Note that the T-MMSE (see 'Telephone\_MMSE') will only be collected (via telephone) from participants who have a confirmed medical diagnosis of dementia.
- Unable to speak and understand English sufficiently well enough to receive the intervention

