# 8 TRIAL PROCEDURES

## 8.1 Participant identification and screening

We propose identifying potential participants via five mechanisms:

1. Through NHS musculoskeletal physiotherapy departments
2. Through NHS musculoskeletal assessment and triage/treatment services (MSK CATS)
3. Through GP practices and First Contact Practitioners (FCPs)
4. Via Social media advert, the University of Salford Hub advert and posters

5. Through a database of volunteers held at the University of Salford

*1 NHS physiotherapy departments – research site*

NHS physiotherapy departments will be set up as research sites with local staff undertaking screening and consenting activity. In situations where local staff have limited capacity for recruiting and consenting, then research staff (at the University of Salford) will screen and consent participants. However, research staff at the University will not have direct access to patient information and will carry out full screening only after the participant has independently contacted the University or has provided consent to contact. With this approach, initial searching of NHS patient records/patient identification will always be undertaken by the patient's direct care team with full screening undertaken by either local site staff or University of Salford staff.

Potential participants in physiotherapy departments will be identified through searching of electronic records or during routine clinical consultation. This consultation will include individual treatment sessions, during group exercise classes or at the point of discharge from NHS clinical services. Electronic searching will be carried out by direct healthcare team members to identify people with a relevant diagnostic (SNOMED CT) code for knee OA. The resulting patient lists will then be screened to rule out patients who do not meet eligibility criteria. Eligible participants will then be sent an invitation letter (see 'Letter of invitation') and participant information sheet (see 'Participant information sheet (Clinical trial)') and asked to contact the local team. The local team may choose to follow-up the initial invitations with a phone call or send a reminder. Participants who contact the local team will undergo full screening following local procedures.

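### Eligibility does not exclude people who have already received CMT, although the trial's own training programme gives CMT to patients found through overlapping recruitment channels

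*Protocol*

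**What the plan says.** **Contamination (Section 6.7).** CMT is described as available only through the university's research studies, followed by "Therefore, at present, it is not possible for patients outside this trial to access this treatment". The risk considered is that control participants might obtain CMT privately while the trial is running. The safeguards are leaving the intervention's name out of the information sheet and asking about physiotherapy used during the trial.

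**Training (Section 6.4).** Two groups of patients receive CMT without being randomised.
- For workshop patients, "we will recruit via non-NHS mechanisms (social media, poster, university database) following the procedures described in Section 8.1". On treatment, "Consenting participants will receive the CMT treatment from the research team before/after the training day and may receive some treatment during the training day".
- After the second workshop, physiotherapists may practise on patients of their own: "These patients will be identified by the physiotherapist as an individual who is currently under their care for knee OA". This is optional.

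The research team keeps the contact details of training patients for the length of the trial.

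**Earlier recipients.** The risk assessment in Section 6.2 states: "To date, we have delivered implementations of the CMT intervention to over 200 participants with no adverse events". Section 10.2 says the feasibility trial randomised 82 people through three MSK CATS departments under the same inclusion and exclusion criteria as this trial.

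**Trial recruitment (Section 8.1).** The five routes include "Through NHS musculoskeletal physiotherapy departments", MSK CATS, social media and posters, and "Through a database of volunteers held at the University of Salford".

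**Eligibility (Sections 7.1 and 7.2).** No criterion mentions earlier receipt of CMT, participation in an earlier CMT study, or physiotherapist training. Section 8.1 has screening carried out against these criteria.

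**The concern.** CMT aims to leave participants with lasting skills: Section 6.2 intends the new muscle patterns to become habit and to support self-management. A control participant who learned those skills earlier does not represent usual care alone. A CMT-arm participant who has already had the course may gain less from repeating it. Both move the estimated difference towards zero.

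The safeguards in Section 6.7 look forward from randomisation and do not detect exposure before it. Prior CMT is also absent from the baseline items listed in Section 8.6, so on the stated plan such participants might not be identifiable later, even for a sensitivity analysis. Baseline healthcare use is collected, but its content is not shown and it is not linked to eligibility.

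Exposure before randomisation is not an intercurrent event, so the treatment policy strategy in Section 10.4 does not address it. It is a question of who belongs in the population, and that is settled by the eligibility criteria.

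**Working it through.** **Step 1. Can a previous recipient be randomised under the plan as written?**

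| Source of prior CMT | How these people are found | Overlapping trial route (Section 8.1) |
|---|---|---|
| Workshop patients (6.4) | Social media, poster, university database | Routes 4 and 5 |
| Practice patients (6.4) | Trial physiotherapists' own knee OA caseload | Route 1, physiotherapy departments |
| Feasibility trial CMT arm (10.2) | MSK CATS, same eligibility criteria | Route 2, same type of service |

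Practice treatment falls in the 1 to 3 months before the final workshop, with timing that depends partly on trial recruitment (Section 6.4). It can therefore come shortly before the same department starts to recruit. No listed criterion stops any of these people. The answer is yes.

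**Step 2. Reproduce the plan's sample size.** Inputs from Section 10.1: baseline mean 41.3, SD 17.8, 20% difference, effect size 0.46, two-sided 5% test, 90% power, 20% attrition.
- Difference: 0.20 × 41.3 = 8.26, stated as 8.3.
- Two-sample t-test at d = 0.46: 100.28, rounded up to 101 per group, as stated.
- Attrition: 101 / 0.80 = 126.25, stated as 126 per group, 252 in all.

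**Step 3. Illustrate the dilution.** Let p be the share of those randomised, equal in both arms in expectation, who have had CMT before. Assume they gain nothing further from being allocated to it. Then:
- expected difference = 8.3 × (1 − p);
- effect size = 0.46 × (1 − p).

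The protocol gives no value for p, so every share below is an assumption. Power is for an unadjusted two-sided t-test with 101 per group.

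| Assumed p | People out of 252 | Difference (points) | Power |
|---|---|---|---|
| 0% | 0 | 8.3 | 90% |
| 3% | about 8 | 8.05 | 88% |
| 5% | about 13 | 7.89 | 87% |
| 10% | about 25 | 7.47 | 83% |

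**Step 4. Allow for baseline adjustment.** Section 10.4 adjusts for baseline WOMAC. If r is the correlation between baseline and 12 months, the effect size becomes 0.46 × (1 − p) / √(1 − r²). The protocol does not give r, so a range is assumed.

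| Assumed p | r = 0.3 | r = 0.4 | r = 0.5 |
|---|---|---|---|
| 5% | 90% | 92% | 95% |
| 10% | 87% | 89% | 92% |

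At 5% the adjusted analysis keeps the planned 90% over this range. At 10% it does so only towards the upper end.

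**The case against.** The case for leaving the criteria alone has real strength.

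- **The numbers are probably small.** There are 12 physiotherapists, practice on patients is optional, and some are expected to practise with colleagues instead. This stands.
- **Existing criteria remove some people.** Entry needs a WOMAC pain score of at least 4 and dissatisfaction with exercise, so those who did well on CMT are less likely to qualify. This stands in part: people still symptomatic after CMT remain eligible.
- **The team could recognise training patients.** It holds their details and does the full screening for several routes. Recognition alone is not enough, because no criterion makes prior CMT a reason to exclude. The same applies to the web screening form, which is not shown: even if it asks, a yes has no consequence under Section 7.
- **The Section 6.7 sentence is loose wording.** The sentence before it acknowledges delivery through research studies, and the section is about access during the trial. This is fair. Taken alone, the sentence needs only a wording correction.

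A reader might infer that the more than 200 earlier recipients form a pool ready to enter. The documents do not support that. The figure covers implementations of CMT in general and is not split by eligibility, place or date. The protocol does not say that the same MSK CATS departments will be used again, or that the Salford database contains former recipients.

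A reader might also infer bias between arms. Prior exposure precedes randomisation and is balanced in expectation, so the expected consequence is dilution, not a spurious benefit.

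**Conclusion.** The gap is real. Following the protocol as written, a person who has already received CMT and meets the listed criteria can be randomised to either arm, and the trial itself treats such people through overlapping channels. The consequence is dilution towards zero and a less clear target population.

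The size is unknown and probably small. The only figure to offer is illustrative: about 3 percentage points of power at an assumed 5% share with no further benefit, before baseline adjustment. Zero further benefit is the unfavourable end of the range, and adjustment could offset much or all of the loss at low shares. The calculation does not show that the trial is underpowered, and the stated 101 and 126 per group stand.

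The change is still worth making. It is cheap, it concerns who enters the trial, and it cannot be fully repaired once people have been randomised.

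**What to change.** 1. Add to Section 7.2 an exclusion for any previous receipt of CMT, whether in an earlier study, as a physiotherapist-training patient, or privately.
2. Add one question on this to the web and telephone screening forms and to the screening done by local teams. It should describe the treatment in plain terms, since the name is deliberately withheld from the information sheet.
3. Check potential participants against the training-patient contact details kept under Section 6.4. Check earlier-study records too if they are still held; the protocol does not say whether they are.
4. Correct Section 6.7 to say that CMT is delivered outside this trial in the university's other research and in physiotherapist training, and that previous recipients are excluded.

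The cost is a protocol amendment with one eligibility line and one screening question, and a very small reduction in the eligible pool. The sample size does not change. If people have already been randomised when the change is made, ask them about earlier CMT so that exposure is at least recorded.
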